
Comparison of NIDA-obtained and dispensary-obtained cannabis effects on NP. We will compare the effect of laboratory cannabis administration and IMPACT self-report data on changes in pain (both measured with NPRS) before and after drug exposure. We will assess pain change scores for the laboratory study and IMPACT measured as the difference between

baseline (before drug) and 60 and 120 minutes after drug, time points that correspond with pain reduction in our prior THC work⁶⁰. We will use the following analyses: 1) plot the distribution of the CBD/THC ratio (x-axis) against pain change (y-axis), calculate the slope of pain change scores for both the lab data and IMPACT, and determine if the slopes are similar or significantly different (a mixed effect model that will estimate changes in outcomes/slopes). 2) If the slopes are nonlinear, we will calculate the area under the curve (AUC) – a measure of total pain change – up to a CBD/THC ratio of 10 (our high CBD dose in the lab). 3) It is possible that our IMPACT data show that many participants only use one or two types of cannabis (e.g., with only a single CBD/THC ratio), thus it might be difficult to plot a CBD/THC ratio distribution. In that event, we will classify IMPACT cannabis use into 3 categories (low CBD/THC ratio, < 1; matched CBD/THC 1:1; high CBD/THC ratio, >1, and examine the correlation between the pain change in each category (averaged over the IMPACT study) with the pain change scores we observe for our low, medium, and high CBD laboratory doses. If our findings indicate a higher slope or greater AUC for NIDA cannabis vs. dispensary cannabis, this would suggest less efficacious pain relief from the local cannabis sources. In contrast, a strong correlation between CBD pain change scores for NIDA and dispensary product in one or more CBD/THC ratio categories would support a consistent finding for the effectiveness of different CBD amounts. In summary, either agreement or discrepancy between NIDA and dispensary data would be highly informative and would help guide future policy recommendations for cannabis-based pain treatment.

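### The fallback lab-versus-dispensary comparison rests on a correlation, which cannot show that the two sources give similar pain relief

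*Combined protocol and SAP*

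**What the plan says.** The comparison paragraph of section 7.2 has three steps. Step 1 compares slopes of pain change on the CBD/THC ratio between the laboratory and IMPACT. Step 2 compares AUC if the relation is nonlinear. Step 3 is for the case where many participants use only one or two products: "thus it might be difficult to plot a CBD/THC ratio distribution. In that event, we will classify IMPACT cannabis use into 3 categories", namely "low CBD/THC ratio, < 1; matched CBD/THC 1:1; high CBD/THC ratio, >1". The analysis is then to "examine the correlation between the pain change in each category (averaged over the IMPACT study) with the pain change scores we observe" for the low, medium and high CBD laboratory doses.

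Two readings are fixed in advance. For slope and AUC: "If our findings indicate a higher slope or greater AUC for NIDA cannabis vs. dispensary cannabis, this would suggest less efficacious pain relief" from local sources. For the correlation, the conclusion on offer is "a consistent finding for the effectiveness of different CBD amounts", and the condition for it is put thus: "a strong correlation between CBD pain change scores for NIDA and dispensary product in one or more CBD/THC ratio categories would support" it. The paragraph adds that either outcome "would help guide future policy recommendations for cannabis-based pain treatment".

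For step 3 the plan gives no cut-off for a strong correlation, no mean difference, no confidence interval, no margin or agreement measure, and no rule for combining three categories. Section 7.1 sets a 5% level for all testing. Section 2.0 lists the comparison among the secondary and exploratory analyses.

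**The concern.** The question is whether the two sources change pain by similar amounts. A correlation answers a different one: whether people with larger changes in one setting also have larger changes in the other.

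Both scores come from the same 0–10 scale in the same people. Someone with more pain, or a habit of wide ratings, will tend to show larger changes in both settings whatever the product. Step 3 states no adjustment for this. A correlation inside a single ratio category also contains no contrast between CBD amounts, although the attached conclusion is about different CBD amounts.

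Followed as written, the rule could therefore report consistent effectiveness for dispensary products that deliver a fraction of the laboratory relief, in a paragraph meant to inform policy. The only stated criterion for weaker dispensary relief is slope or AUC. Those belong to steps 1 and 2, and step 3 is used when the ratio distribution they rest on is hard to plot.

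**Working it through.** **Plan's own figure.** No power or precision is stated for this comparison. The only Aim 2 figure (section 7.4) is R = 0.218 at 80% power, for the association of exposure predictors or HRV with pain change. With f² = R²/(1−R²), a noncentral F and two-sided α = 0.05, an effective n of 160 gives R = 0.2175, and power at 0.218 is 80.2%. The figure reproduces, but it concerns another analysis.

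**Exact part, no assumptions.** Let L be laboratory change and D dispensary change. For any f > 0 and constant c, corr(L, c + fD) = f·Cov(L, D) / (SD(L)·f·SD(D)) = corr(L, D). If D = fL exactly, r = 1.00 for f = 1, 0.5, 0.25 or 0.1. In a sample with mean laboratory relief of 1.89 points, mean dispensary relief is then 1.89, 0.95, 0.47 and 0.19.

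**Illustration A: baseline pain is the only link (assumed inputs).** Baseline mean 5, SD 2, clipped to 0–10; laboratory change = a × baseline + noise of SD 1; IMPACT average = b × baseline + noise of SD 0.32; a = 0.4, so laboratory relief is 2.0 points. Without clipping, r = 4ab / √[(4a² + 1)(4b² + 0.32²)]:

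- b = 0.1 (0.5 points, 25%): 0.16 / √(1.64 × 0.1424) = 0.33
- b = 0.2 (1.0 point, 50%): 0.32 / √(1.64 × 0.2624) = 0.49
- b = 0.4 (2.0 points, 100%): 0.64 / √(1.64 × 0.7424) = 0.58

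Clipping brings these to 0.33, 0.48 and 0.57. Simulated chance of meeting the rule in one category (runs differ by about one percentage point):

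| Dispensary relief | r ≥ 0.5, n = 80 | p < 0.05, n = 80 | r ≥ 0.5, n = 27 |
|---|---|---|---|
| 25% of laboratory | 3% | 86% | 15% |
| 50% | 43% | 99.6% | 47% |
| 100% | 84% | 100% | 72% |

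Here n = 80 is the completer number in section 7.4, all in one category; n = 27 is 80 split over three. The smallest r significant at 5% is 0.22 at n = 80 and 0.38 at n = 27.

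**Illustration B: shared-trait correlation held at 0.7 (assumed).** Mean laboratory relief 2, SD 1.5, dispensary scores scaled by f. At n = 80, mean r is 0.70 and P(r ≥ 0.5) is 99.8% for f = 1, 0.75, 0.5 and 0.25. With zero mean dispensary relief and the same SD, P(r ≥ 0.5) is still 99.7%.

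**Any one of three categories.** If *strong* means significant at two-sided 5%, and three independent categories have no true correlation, the chance of at least one significant positive correlation is 1 − 0.975³ = 7.3%.

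**What a paired difference would show.** The 95% CI half-width is t × 1.5 × √[2(1−ρ)] / √n. For ρ = 0.7 to 0.5 with equal SDs of 1.5 (assumed), that is 0.26 to 0.33 points at n = 80 and 0.46 to 0.59 at n = 27. In Illustration B at f = 0.5, the 1.0-point shortfall is detected by a paired t-test in over 99% of trials at either n.

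**Laboratory ratios, from section 4.1.** Low: 0.01/1.9 = 0.005. Medium, if vial masses are equal: (0.01 + 5.1)/(1.9 + 1.4) = 1.55. High: 5.1/1.4 = 3.64. Two doses exceed 1 and none is 1:1. Section 7.2 also associates the high laboratory dose with a ratio of 10, which does not match 3.64.

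**The case against.** The plan asks for a *strong* correlation, not merely a significant one. A reader might infer that the rule hardly separates a fourfold shortfall from equal relief. Illustration A does not support that if strong means r ≥ 0.5: the rule is then met in about 3% of trials against 84%. It comes close to that only if strong means significant (86% against 100%) or if a shared trait holds r constant. The documents settle neither, so the general claim cannot be made.

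A reader might also put the false-positive chance at 1 − 0.95³ = 14%. That counts negative correlations, which would not support consistency, and it needs three populated categories, so it cannot be combined with a calculation that puts all 80 people in one.

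Nor does the plan say that equal relief with little spread between people would be called disagreement; it attaches no conclusion to a weak correlation. Correlation across persons within a category is itself the natural reading rather than stated text.

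There is partial cover elsewhere. The models in sections 7.1 and 7.2 should yield the size of relief in each setting, so a careful author would see a large gap. The comparison is secondary, step 3 is conditional, and the wording is only that the result would support a conclusion.

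These points limit the size and weight of the problem. They do not remove it: nothing in step 3 turns those separate results into a comparison of relief. *Consistent* could mean consistent ranking of people, but the sentence is set against less efficacious relief and speaks of effectiveness.

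**Conclusion.** The point holds for step 3 of a secondary/exploratory comparison; no primary aim depends on it. The correlation cannot establish similar relief from the two sources, and one within a single category cannot speak to different CBD amounts. That part is exact and rests on no assumed value. The frequency of a misleading conclusion is not determined by the documents: it depends on what *strong* means and on change-score means, SDs and correlations that are not given. Under the assumed models, the chance of meeting the rule in one category at n = 80 when dispensary relief is a quarter of laboratory relief runs from about 3% to 99.8%. The change is worth making because the paragraph looks ahead to policy use and the plan itself expects that the fallback may be needed.

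**What to change.** In step 3, base the conclusion on the within-person difference in pain change (laboratory minus IMPACT) per category with a 95% CI. Estimate it from a mixed model with setting, category and setting × category terms and pre-use pain as covariate. Judge consistency from the size of that difference across the categories that have data, not from any single one. Keep the correlation as descriptive.

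Before pairing, reconcile the three ratio categories with the laboratory dose ratios, since no dose falls in the 1:1 category as the contents are stated. State also that the difference reflects product and amount together: section 4.2 fixes the laboratory amount, whereas dispensary use is self-chosen.

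No new data are needed. Both scores are on the NPRS, in the same participants, at 60 and 120 minutes. The cost is revised SAP text plus the category reconciliation, which is more than a change of wording. The downside is that agreement becomes harder to claim where a category has few participants.

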7.3 Aim 3 Measures and Analyses

We will use a linear model to examine the association between the total CBD, THC, and CBD/THC ratio during IMPACT and the change in NP, disease markers (CD4, viral load, Total Neuropathy Score, and neurocognitive global T-score), and EC biomarkers (AEA, 2-AG, FAAH, MAGL, CB2) from baseline to the final visit after month 6. We will control for confounders as in Aims 1 and 2, including any CBD and THC levels recorded at the baseline and final sessions. Linear models will compare the month 6 – baseline change in pain and in EC biomarkers between the heavy- and light-cannabis groups. One exploratory analysis will test for an interaction between group (light vs. heavy) and CBD and THC levels on change in NP and EC biomarkers. We will assess if exposure mode (smoking/vaporizing/ingestion) predicts pain outcome. We will examine if there is an association between pain change over time and changes in EC biomarkers. During the 6-month IMPACT, alterations may occur in cannabis use or pain medication (e.g., a person enrolled as a light cannabis user may start to engage in heavy use or begin using non-cannabis medication for pain, i.e., an opiate, which we will record with IMPACT). To address these issues we will conduct light vs. heavy use analyses based both on the baseline group classification and the actual use during IMPACT, include a cannabis use 'change' factor in the analyses (going from light to heavy use, or vice versa), and include the initiation of any non-cannabis pain medication as a factor in the model.

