4.3. IMPACT

All participants will be instructed on how to use the IMPACT text messaging/website survey program, practice the SMS interface with study staff, and set up personalized preferences (e.g., optimal times to receive messages). If they do not have a cell phone capable of receiving and sending text and picture messages, one will be provided to them at the baseline session and we will purchase bulk 'minutes' in order to provide the text message intervention. Participants will also receive digital milligram scales that they can use to weigh out cannabis products, including joints, blunts, and bowls. Participants will not be required to use the scales, but they will be provided as an optional tool to improve the accuracy of reporting cannabis quantity. Participants will not be responsible should they lose or break the devices. We will also ask participants to identify the source of their cannabis products, including the name of the medical dispensary where the product was obtained. If the participant obtained cannabis from another source, such as a neighbor or friend, this source will be anonymously identified as "friend". We will not collect any names or any identifying information about any specific individuals who provide cannabis to the participant; only the names of medical dispensaries in San Diego will be collected. Participants will also not be required to disclose the source of the cannabis and may select an option of "decline to provide" or "I do not know" or "unknown" when asked about this information. (45 minutes). After the 6-month IMPACT is completed, participants will return for a visit that will include the same assessments during the pre-entry visit, including a medical exam with neuropathy testing, assessment of substance use, administration of pain rating scales, neurocognitive testing, and a blood draw to repeat baseline evaluations including THC, CBD, and EC biomarkers and check hepatic/renal function. We will not administer cannabis at this session, and similar to the pre-entry visit, request that participants abstain from cannabis for 24 hours before this visit.

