
time point. All response observations, including information from subjects who do not complete all experimental sessions, will be included in the analyses. Similar mixed-model analyses will be performed on the primary pain outcome after adjustment for psychomimetic side effects (measured with the ARCI scale) to assess for effects of the study drug on pain independent of subjective responses. The proportion of subjects with a 30% pain reduction, a standard for effective pain reduction⁶⁰ will be compared between each of the doses with chi-square tests; we will also calculate the number needed to treat (NNT) for a 30% pain reduction rate. We will also conduct analyses to examine the association between pain and EC biomarkers, including AEA, 2-AG, FAAH, and MAGL expression. A 5% significance level will be used for all testing. The association of pain levels with HRV will use a linear mixed-effects model, adjusting for potential confounders as above. Within-subject correlation will be accounted for using subject-specific random intercepts and slopes.

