For Aim 2, with 20% attrition over the 6 months of IMPACT we have $n= 80$ participants with 6 months (26 weeks) of data. We conservatively ignore the drop-out participants (who nonetheless contribute partial data). Assume, conservatively, that participants will use cannabis on average 2 times/week. This gives $n=80$ and $k=52$ observations/participant. If ICC is the intra-class, or within-participant correlation, the effective sample size (number of equivalent independent observations) is $n_{\text{eff}} = n/(ICC+(1-ICC)/k) \approx n/ICC$ [e.g., Killip, Mahfoud, Pearce, Ann Fam Med, 2004; 2:204-208.]. Assuming conservatively $\rho=0.5$ (or lower), we get $n_{\text{eff}} = 2n = 200$ [$n_{\text{eff}} = 160$]. We have 80% power to detect a (partial) correlation R between the individual predictors (Hypothesis 1: CBD, THC, and the CBD/THC ratio; Hypothesis 2: pain levels and HRV) and change in pain of $R = 0.218$ (or semi-partial $R^2 = 0.0475$), after adjusting for confounders. Calculations used G*Power.

For Aim 3, assuming $n = 80$ participants complete the 6-month follow-up, we have 80% power to detect an association between an individual predictor and response (e.g., total CBD and changes in neuropathic pain levels) of $R = 0.302$ (or semi-partial $R^2 = 0.092$), after adjusting for confounders. The calculations used G*Power.

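### Aim 3 treats final-visit CBD and THC levels as confounders of the six-month CBD/THC total, although they are measured after that exposure and partly produced by it

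*Combined protocol and SAP*

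**What the plan says.** Section 7.3 specifies a linear model for "the association between the total CBD, THC, and CBD/THC ratio during IMPACT and the change in NP", with disease markers, neurocognition and endocannabinoid biomarkers as further change outcomes. It carries over the confounders from Aims 1 and 2 and adds CBD and THC levels, "including any CBD and THC levels recorded at the baseline and final sessions".

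Later in the same section, in the sentence on light versus heavy use, the plan adds a factor for moving between light and heavy use and says it will "include the initiation of any non-cannabis pain medication as a factor in the model".

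Section 4.3 places the final blood draw, which includes THC, CBD and endocannabinoid biomarkers, after IMPACT is completed. It says staff will "request that participants abstain from cannabis for 24 hours before this visit".

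Section 7.4 gives the Aim 3 power: "assuming $n = 80$ participants complete the 6-month follow-up, we have 80% power to detect an association" between one predictor and the response "of $R = 0.302$ (or semi-partial $R^2 = 0.092$), after adjusting for confounders".

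Section 7.3 gives no reason for including the final levels and plans no model without them.

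**The concern.** A confounder of the six-month total must precede that total or share a cause with it. A blood level taken after the six months is a downstream marker of recent, and to some extent cumulative, use. Holding it fixed asks how the total relates to outcome among people who end with the same circulating level. That differs from asking how six months of use relates to change in pain or biomarkers.

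Two things can follow. If the final level only tracks use and has no relation to outcome of its own, the coefficient stays unbiased but is estimated from less exposure variation. If the final level carries part of the effect, that part is removed. The second case is plausible for the biomarkers. Section 1.1 says CBD may raise AEA by inhibiting uptake and FAAH activity, and section 4.3 takes cannabinoid and endocannabinoid measures from the same draw.

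Medication initiation also arises after exposure begins and may follow worsening pain, which is the outcome. Section 2.0 lists Aim 3 among the primary outcome measures, although the opening summary calls the analyses of pain over time exploratory. With no unadjusted comparison planned, a null Aim 3 result could not be told apart from over-adjustment.

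**Working it through.** **Inputs from the documents.** n = 80 and 80% power (7.4); R = 0.302 (7.4); 5% significance level (7.1), taken as two-sided because sidedness is not stated.

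**Assumed inputs.** The documents do not give the correlation *a* between final level and six-month total, the share *m* of the association carried by the final level, or the rate and causes of medication start. Ranges are used below.

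**1. The plan's own figure.** For one regression coefficient, f² = R²/(1 − R²) = 0.0912/0.9088 = 0.1004. The noncentrality is √(n·f²) = √(80 × 0.1004) = 2.83, with n − k − 1 degrees of freedom. Power is 0.799 with k = 1 predictor and 0.796 with k = 20. The detectable R is 0.302 to 0.303 across that range. The stated figure reproduces, and the number of covariates hardly matters.

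**2. Final level as a pure proxy.** Suppose the total association is 0.302 and the final level has no relation to outcome of its own. The coefficient is unchanged, and exposure variance shrinks by (1 − a²). Then f² = R²(1 − a²)/(1 − R²), with 77 degrees of freedom.

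| a | variance inflation 1/(1 − a²) | semi-partial R = 0.302√(1 − a²) | f² | power |
|---|---|---|---|---|
| 0.3 | 1.10 | 0.288 | 0.0913 | 76% |
| 0.5 | 1.33 | 0.262 | 0.0753 | 68% |
| 0.7 | 1.96 | 0.216 | 0.0512 | 52% |
| 0.8 | 2.78 | 0.181 | 0.0361 | 39% |

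**3. Final level carries a share m of the association (a = 0.5).** The remaining coefficient is 0.302(1 − m). The final level's own coefficient is b = 0.302m/a. The full-model R² is 0.302² + b²(1 − a²), and f² = [0.302(1 − m)]²(1 − a²)/(1 − full R²).

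| m | remaining coefficient | full R² | f² | power |
|---|---|---|---|---|
| 25% | 0.2265 | 0.108 | 0.0432 | 45% |
| 50% | 0.151 | 0.160 | 0.0203 | 24% |
| 75% | 0.0755 | 0.245 | 0.0057 | 10% |

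Steps 2 and 3 use one final level. With several, *a* is read as the multiple correlation.

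**4. Medication initiation (simulation, 2,000,000 draws; coefficients in absolute value).**
- Start driven only by worsening pain (20–35% start; log-odds slope 0.5 to 2 per SD of pain change): adjustment shrinks the coefficient from 0.303 to between 0.29 and 0.20, and power is 79% to 62%.
- Start triggered by worse pain, and the drug then lowers pain by 1 SD (25% start): the coefficient moves from 0.255 to 0.265.
- An independent analgesic effect of 0.6 SD, used more by low-exposure participants (25% start): adjustment restores the coefficient from 0.248 to the true 0.302. If use is unrelated to exposure, the coefficient stays at 0.302.

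The direction for medication is therefore not fixed.

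**The case against.** The strongest reply concerns power. A reader might infer that the 80% figure in 7.4 is wrong. It is not: 7.4 states R = 0.302 as an association after adjustment, already net of overlap with the covariates, and it reproduces. What remains is narrower. The adjusted association must itself reach 0.302, and a total association of that size may not leave that much once final levels are in the model.

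A reader might also infer that the adjustment certainly removes part of the association. The documents do not support that either. In the pure-proxy case only precision is lost, and nothing in the plan shows how much of the effect the final level carries. One sample after requested abstinence, in a population that includes people using 1–4 times a month, may correlate only weakly with a six-month total. At 0.3 the loss is about four points of power.

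There is a reasonable purpose for the final levels: separating drug present at testing from chronic exposure. The 24-hour abstinence in 4.3 is requested, and no check on it is stated there, so the request does not make that purpose redundant. But 7.3 does not state the purpose, and a sensitivity model would serve it.

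On medication, the objection largely stands. A newly started analgesic is a co-intervention, and leaving it out can credit its effect to cannabis. The worsening-pain argument does not apply directly to CD4, viral load, neurocognition or the biomarkers. The sentence belongs to the light/heavy analyses, so its reach into the total CBD/THC model is uncertain. That sentence also commits to analyses by both baseline group and actual use, which is a partial safeguard.

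**Conclusion.** The point holds for the final-visit levels. They cannot confound a total accumulated before they were measured, and the plan offers no model without them. For a total association of 0.302, power falls from 80% to roughly 76%, 68% or 52% at assumed pure-proxy correlations of 0.3, 0.5 or 0.7. If the levels also carry part of the effect, the coefficient itself shrinks. These sizes rest on assumed correlations and shares, and on the levels actually entering the model; 7.3 does not say whether the α = 0.20 screen of 7.1 applies to them.

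It does not follow that the stated power is miscalculated, that attenuation is certain, or that adjusting for new medication biases the result in a known direction. For medication, the supportable request is that the plan say which model the term enters and why. Baseline CBD and THC levels are not in question.

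**What to change.** State in 7.3 that the main Aim 3 model adjusts for pre-exposure covariates only: the baseline value of the outcome, baseline CBD and THC levels, and the baseline confounders. Report as labelled sensitivity analyses the models that add (a) final-visit CBD and THC levels, with recent use at testing given as the reason, (b) initiation of non-cannabis pain medication, and (c) the factor for change between light and heavy use. State whether (b) is meant for the total CBD/THC model, the light/heavy model, or both.

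The cost is a change of SAP wording and one or more extra model runs. Data collection and sample size stay as they are, and the n = 80, R = 0.302 statement can stand. The main estimate will no longer separate residual drug at the final visit from chronic exposure; model (a) addresses that.
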